- b. Subjects will report to the study site 10 times during the Induction Phase (9 patch applications). The patches will remain in place for 48 (±2) hours during the week. Patches applied on Friday will remain in place for approximately 72 (±2) hours until Monday.
- c. 30 minutes (up to 1 hour) after each patch removal, a trained blinded assessor will perform an assessment of all test sites for irritation symptoms using the scoring system detailed in Appendix 2.
- d. A trained (by a dermatologist) blinded assessor will perform assessments of all test sites for symptoms of irritation using the scoring system detailed in Appendix 2.
- e. Visit 11 (Day 22) will be the final Induction Phase patch removal and grading/assessment.
- f. Challenge Phase patch application (after 2 week Rest Phase), Visit 12 (Day 36). The challenge patch will be applied to a naïve site and remain in place for 48 (±2) hours.
- g. Visit 2 (Day 1) Baseline assessments of the patch sites will be performed prior to the patch application.
- h. Visit 12 (Day 36) assessments of the naïve challenge patch site will be performed prior to the challenge patch application.
- i. 30 minutes (up to 1 hour) following Challenge patch removal a trained blinded assessor will perform an assessment of the Challenge test site for irritation symptoms using the scoring system detailed in Appendix 2.
- j. Further evaluations of naïve patch removal site will take place 24 (±2) and 48 (±2) hours after patch removal (e.g., apply the patch on Monday, remove the challenge patch on Wednesday, and evaluate the sites on Wednesday, Thursday and Friday).
- k. Subjects are asked to report any adverse events from Visit 2 (or Visit 1 if patch application occurs at Visit 1) and the use of any concomitant medications throughout the study.

| Document Name | GSiki28/7985iqurot2007 585 | | |
|----------------------|---------------------------------------|---------------------|----------------------|
| Туре | Version | Document Identifier | Effective Date |
| eldo climitralleatoc | 0.0; CURRENT; Most-Recent; Registived | 090032d580e4@556 | 31-Jan-2017 14:20:06 |
| Reason For Issue | Auto Issue | | |

PROTOCOL SYNOPSIS FOR STUDY 207585

Brief Summary

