6.2.2 Patch Assessments

An experienced trained assessor (s) will assess all patch sites for the duration of the study according to the scoring scale in Appendix 2. Each patch will be removed and the treated areas will be cleaned with saline solution before visual assessment. Where ever possible the same experienced trained assessor will perform all skin assessments for a given subject at each assessment time point.

A Baseline patch site assessment will be carried out at Visit 2 (or Visit 1 if visits combined) prior to any patch application. Patch assessments will then be performed at Visits 3 to 11 for the Induction Phase (every 48 ± 2 hours following application). After the last grading/evaluation of the Induction Phase at Visit 11, subjects will enter a Rest Phase of 2 weeks.

| Document Name | ©\$\\\\\\\\\\\\\\\\\\\\\\\\\\\\\\\\\\\\ | | |
|-----------------------|---|---------------------|----------------------|
| Туре | Version | Document Identifier | Effective Date |
| eldo climitarelleatoc | 0.0; CURRENT; Most-Recent; Revietived | 090032d580e42d66 | 31-Jan-2017 14:20:06 |
| Reason For Issue | Auto Issue | | |

After completing the Rest Phase, subjects will return for the Challenge Phase (Visit 12). Prior to the Challenge patch application the naïve patch sites will be assessed. The challenge patch will be randomly applied to previously untreated areas of skin for 48 ± 2 hours. After on-site patch removal (Visit 13), the patch site will be cleaned with saline solution and graded/evaluated after 30 minutes (maximum of 1 hour). Subjects will return for further assessments after 24 ± 2 hours (Visit 14) and 48 ± 2 hours (Visit 15) post patch removal for further grading/assessment.

Patch sites will be graded using a magnifying glass with a fluorescent daylight lamp. The assessor will be blinded to the treatment allocation location.

The results will be presented as individual responses to each test product at each assessment time point.

In any case of a positive reaction a dermatologist will be available to perform secondary assessments and grade the response with any further action as needed. This should occur the same day as the initial assessment performed by the trained assessor.

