Protocol: 207585

Program Run Date:ddmonyyyy

Table 14.2.1.1
Frequency of Combined Score by Phase, Visit and Treatment and Maximum Combined Score
Intent to Treat Population

Intent to Treat Population (N=XX)

Phase: Induction Phase

Visit	Combined Scores	Facial micellar cleanser		Saline Solution	
		(N=XX)	n	(N=XX)	n
Subjects with at least one combined score > 0 at any visit n (%)		xx (xx.x)		xx (xx.x)	
Subjects with no combined score > 0 at any visit n (%)		xx (xx.x)		xx (xx.x)	
VISIT 2	0	xx		xx	
	1	xx		xx	
	2	xx		xx	
	3	xx		xx	
	4	xx		xx	
	5	xx		xx	
	6	xx		xx	
	7	xx		xx	
VISIT 3		xx		xx	
		xx		xx	
		xx		xx	
VISIT 10		xx		xx	
		xx		xx	
MAXIMUM COMBINED SCORE	1	xx		xx	
	2	xx		xx	
	3	xx		xx	
	4	xx		xx	
	5	xx		xx	
	6	xx		xx	
	7	xx		xx	

Combined Score: Dermal response Score + Superficial response score (>0)

Page x of y

PPD

Programming Note:

- Induction Phase include visit 2 till visit 10.
- Rest Phase include Visit 11
- Challenge Phase include visit 12 till visit 15
- This table is only required if at least one subject reports a combined score >0
- Maximum combined Score will be calculated and displayed at the end of each phase irrespective of visits.

Document Name	gsk-207585-reporting-and-analysis-plan		
Type	Version	Document Identifier	Effective Date
eldo_controlled	0.1; CURRENT; Most-Recent; Reviewed	090032d580e125d0	
Reason For Issue			

Protocol: 207585

Program Run Date:ddmonyyyy

Table 14.2.2.1
Frequency of Dermal Response Score by Phase, Visit and Treatment and Maximum Dermal Response Score
Intent to Treat Population

Intent to Treat Population (N=XX)

Phase: Induction Phase

Visit	Score	Facial micellar cleanser	Saline Solution
		(N=XX)	(N=XX)
		n	n
Subjects with at least one dermal response score > 0 at any visit n (%)		xx (xx.x)	xx (xx.x)
Subjects with no dermal response score > 0 at any visit n (%)		xx (xx.x)	xx (xx.x)
VISIT 2			
0		xx	xx
1		xx	xx
2		xx	xx
3		xx	xx
4		xx	xx
5		xx	xx
6		xx	xx
7		xx	xx
VISIT 3			
VISIT 4			
.....			
VISIT 10			
MAXIMUM DERMAL RESPONSE SCORE		xx	xx
.....			

0 = No evidence of irritation; 1= Minimal erythema barely perceptible; 2 = Definite erythema; readily visible;or minimal edema; minimal popular response; 3 = Erythema and papules;4 = Definite edema; 5 = Erythema, edema and papules; 6 = Vesicular eruption; 7 = Strong reaction spreading beyond test site

Page x of y

Programming Note:

- Induction Phase include visit 2 till visit 10.
- Rest Phase include visit 11
- Repeat for the challenge phase.

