Document Name	gsk-207585-reporting-and-analysis-plan		
Type	Version	Document Identifier	Effective Date
eldo_controlled	0.1; CURRENT; Most-Recent; Reviewed	090032d580e125d0	

Protocol: 207585

Program Run Date:ddmonyyyy

Listing 16.1.7
Randomisation information
Randomised Population

Subject Number	Age/Sex/Race[1]	Randomisation Number	Test Site/Treatment Randomised	Date of randomization
PPD				

[1] Age in years; Sex: F = Female, M = Male; Race: A = Asian, B = Black or African American, I = American Indian or Alaska Native, H = Native Hawaiian or Other Pacific Islander, W = White, O = Multiple.

Page x of y

PPD

Document Name	gsk-207585-reporting-and-analysis-plan		
Type	Version	Document Identifier	Effective Date
eldo_controlled	0.1; CURRENT; Most-Recent; Reviewed	090032d580e125d0	

Protocol: 207585

Program Run Date:ddmonyyyy

Listing 16.2.2
Individual Subjects Protocol Violation
Randomised Population

Subject Number	Age/Sex/Race[1]	Phase/Visit # [2]	Violation Sequence	Protocol Violation	
PPD					

[1] Age in years; Sex: F = Female, M = Male ; Race: A = Asian, B = Black or African American, I = American Indian or Alaska Native, H = Native Hawaiian or other Pacific Islander, W = White, O = Multiple.

[2] Induction phase: Visit 2 till Visit 10; Rest: Visit 11; Challenge phase: Visit 12 till visit 15.

Page x of y

PPD

■

Document Name	gsk-207585-reporting-and-analysis-plan		
Type	Version	Document Identifier	Effective Date
eldo_controlled	0.1; CURRENT; Most-Recent; Reviewed	090032d580e125d0	

Protocol: 207585

Program Run Date: ddmonyyyy

Listing 16.2.7.1
All Adverse Events
Randomised Population

Treatment Group: Facial micellar cleanser

Subject Number	Age/Sex/Race [1]	Adverse Event (Preferred Term) (System Organ Class)	Start Date /Study Day [2]	Start Time	End Date	End Time	Frequency /Intensity [3]	Related to Study Product?	Action Taken re Study Product	Outcome	Serious ?	Withdrawn? [4]
PPD												

[1] Age in years; Sex: F = Female, M = Male ; Race: A = Asian, B = Black or African American, I = American Indian or Alaska Native, H = Native Hawaiian or Other Pacific Islander, W = White, O = Multiple.

[2] Study day is the day relative to start of treatment, day 1 being the day of first treatment.

[3] INT = Intermittent and SGLE = Single.

[4] Did subject withdraw from study as a result of this adverse event?

Page x of y

PPD

Programming Note:

- Repeat the same layout for the listing 16.2.7.2
- Population should be used 'Non randomised Subjects'

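### The SAP table shells file the reading after the ninth induction patch (Visit 11) under Rest, so the induction maximum and any-response count use 8 of the 9 post-removal readings

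*SAP*

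**What the plan says.** **The table shells (SAP 5.1).** The programming note to Table 14.2.1.1 reads "Induction Phase include visit 2 till visit 10", then "Rest Phase include Visit 11", and gives Visits 12 to 15 to Challenge. It adds: "Maximum combined Score will be calculated and displayed at the end of each phase irrespective of visits". The printed shell is headed as the induction phase, its visit rows end at Visit 10, and its first row counts subjects with any combined score above zero. The notes to Tables 14.2.2.1 and 14.2.2.2 use the same split and add "Repeat for the challenge phase". The footnote to Listing 16.2.2 repeats it: "Induction phase: Visit 2 till Visit 10; Rest: Visit 11; Challenge phase: Visit 12 till visit 15".

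**Where Visit 11 is an induction reading.**
- Protocol, Schedule of Events, note e: "Visit 11 (Day 22) will be the final Induction Phase patch removal and grading/assessment". Note b counts ten induction attendances for nine patches.
- Protocol 6.2.2: "Patch assessments will then be performed at Visits 3 to 11 for the Induction Phase", and then "After the last grading/evaluation of the Induction Phase at Visit 11, subjects will enter a Rest Phase of 2 weeks".
- The induction headings in the synopsis, protocol 3.1 and SAP 1.1 run from Visit 2 to Visit 11.
- SAP 1.3 describes the two-week rest as free of both patching and assessment.

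**What is to be summarised.** Protocol 9.3.2 and SAP 2.4.1.1 ask for results at each time point and for phase-level results in induction and challenge. Neither plans a rest-phase summary. SAP section 3 reports no departure from the protocol's analysis.

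**The concern.** The reading at Visit 11 follows removal of the ninth induction patch. If the program takes the induction maximum over Visits 2 to 10, that reading cannot contribute to it, nor to the count of subjects with any response in the induction block. A subject whose first reaction appears at Visit 11 would be shown as having no induction response. A subject whose worst reaction is at Visit 11 would be shown with too low a maximum.

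The study is meant to detect irritation under repeated exposure, and protocol section 1 names cumulative effect as something such studies must take into account. The excluded reading is the one with the most cumulative exposure.

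Other outputs would not readily make this good. Responses gradable on Appendix 2 are generally not recorded as adverse events (protocol 6.2.2 and 7.1.1), and SAP 4.3 lists no by-subject score listing.

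**Working it through.** **1. The plan's own count.** Protocol 3.4 counts 1 baseline reading, 8 in induction, 1 in rest (described there as belonging to the last induction removal) and 4 in challenge. 1 + 8 + 1 + 4 = 14, which matches the 14 visits from Visit 2 to Visit 15. The total is right; the question is the phase of the single rest reading.

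**2. Readings available and used** (days from the Schedule of Events).

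| Patch | Applied (visit, day) | Removed and read (visit, day) | Nominal wear, h | Cumulative, h | In shell's induction block? |
|---|---|---|---|---|---|
| 1 | V2, 1 | V3, 3 | 48 | 48 | yes |
| 2 | V3, 3 | V4, 5 | 48 | 96 | yes |
| 3 | V4, 5 | V5, 8 | 72 | 168 | yes |
| 4 | V5, 8 | V6, 10 | 48 | 216 | yes |
| 5 | V6, 10 | V7, 12 | 48 | 264 | yes |
| 6 | V7, 12 | V8, 15 | 72 | 336 | yes |
| 7 | V8, 15 | V9, 17 | 48 | 384 | yes |
| 8 | V9, 17 | V10, 19 | 48 | 432 | yes |
| 9 | V10, 19 | V11, 22 | 72 | 504 | **no** |

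There are nine post-removal readings, of which eight are used. Total nominal wear is 6 × 48 + 3 × 72 = 504 h. At the last reading counted it is 504 − 72 = 432 h, and 432/504 = 86%. Visit 11 is one of the three readings taken after 72-hour wear (Visits 5, 8 and 11).

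**3. Can a reader rebuild the induction result from the two blocks?** Not exactly. Suppose *a* subjects have a response in the induction block and *b* in the rest block, out of *N*. The number with any response at either lies between max(*a*, *b*) and min(*a* + *b*, *N*), because one subject may appear in both. The table does not show the overlap.

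**4. Possible size, by assumption.** The documents give no rate for a first induction response at Visit 11. Let that rate be *q* and take the 200 evaluable subjects. The expected number missed is 200*q*, and the chance of at least one is 1 − (1 − *q*)^200.

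| *q* (assumed) | Expected missed | Chance of at least one |
|---|---|---|
| 0.1% | 0.2 | 18% |
| 0.5% | 1 | 63% |
| 1% | 2 | 87% |
| 2% | 4 | 98% |

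This range is illustrative and is not an estimate for this product.

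**5. Two minor points in the same shells.**
- *Pre-patch readings.* Induction and challenge together hold 9 + 4 = 13 visits. Two of them, Visits 2 and 12, are graded before patching (schedule notes g and h), yet they fall inside the phase maxima, while SAP 2.4.1.1 defines the endpoint on post-removal scores. This matters only if a pre-patch score is non-zero.
- *Score rows.* The scales footnoted to Tables 14.2.2.1 and 14.2.2.2 run from 0 to 7 and from 0 to 3, so the combined score can reach 7 + 3 = 10. The rows of Table 14.2.1.1 stop at 7. With dermal scores 1 to 7 and superficial values 0 to 3 there are 7 × 4 = 28 pairs. Six exceed 7 (5+3, 6+2, 6+3, 7+1, 7+2, 7+3), giving scores of 8, 9 and 10 with no printed row. These are counts of possible values, not likelihoods.

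**The case against.** **The shells follow protocol text.** Protocol 3.4 does count one reading in the rest phase. The schedule header gives Rest as Weeks 4–5, and Day 22 opens Week 4. The Rest headings in the synopsis, protocol 3.1 and SAP 1.1 start at Visit 11. This explains the label but does not justify it. The count in 3.4 itself ties the reading to the last induction removal, and the rest paragraph of the same section starts Rest after that grading. The headings mark the ends of an interval: they share Visit 12 with Challenge in the same way, and assign no reading to Rest.

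**The any-response row may be study-wide.** It counts scores above zero at any visit, and SAP 2.4.1.1 uses similar words without naming a phase. On that reading the row would already include Visit 11. However, it sits in a shell headed as the induction phase, and protocol 9.3.2 asks for any response by phase, so the per-phase reading is the natural one. The maximum is affected either way.

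**Nothing goes unreported.** Protocol 9.3.2 also asks for results at each time point and a narrative of all skin responses. This stands in part. In Table 14.2.1.1 the Visit 11 data should appear in a rest block with its own maximum. In the two component tables, whose notes name Rest but ask only for a repeat for challenge, the display is unclear. Narratives would help, but the SAP's output list contains none, and they would not correct the tabulated maximum.

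**The exposure figures do not measure missed reactions.** This is true. They also assume every patch was worn at one site, whereas protocol 5.2 moves or stops patching after a combined score of 3 or more. The Listing 16.2.2 footnote changes no score summary, and Visit 11 has no bearing on the challenge summaries.

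**Conclusion.** The concern holds and should be fixed. Taken literally, the programming notes give an induction maximum, and on the natural reading an induction any-response count, based on 8 of 9 post-removal readings. They leave out the reading after all nine patches, at 504 nominal hours against 432. This contradicts schedule note e, protocol 6.2.2, the induction heading in SAP 1.1 and the description of the rest period in SAP 1.3, and it affects the primary top-line table.

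The consequence is limited. The reading is displaced, no test or threshold depends on it, and the number of subjects affected cannot be derived from the documents. The any-response part rests on reading that row as per phase; the maximum does not. The pre-patch visits and the missing score rows are secondary.

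**What to change.** In the notes to Tables 14.2.1.1, 14.2.2.1 and 14.2.2.2 and in the Listing 16.2.2 footnote, assign Visit 11 to Induction, remove the Rest entry, and extend the induction visit rows to Visit 11. State that the induction maximum and any-score-above-zero count run over Visits 3 to 11, and the challenge ones over Visits 13 to 15.

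In the same edit, show Visits 2 and 12 as baseline rows outside the phase summaries, and extend the score rows of Table 14.2.1.1 from 7 to 10.

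Reconcile the reading count in protocol 3.4 and the schedule header with note e and protocol 6.2.2. The Rest headings in the synopsis, protocol 3.1 and SAP 1.1 can be aligned at the same time. They are less pressing, since they assign no reading to Rest.

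The cost is wording in three shells and one footnote, plus up to five phase labels. No data, visits or procedures change. The SAP is to be finalised before database freeze and unblinding, so the shell correction belongs in that finalisation.

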Adverse Events (AE) will be tabulated according to the current version of the Medical Dictionary for Regulatory Activities (MedDRA). Frequencies and percentages will be presented overall, for each system organ class, and for each preferred term. Summaries of treatment-emergent AEs, treatment-related AEs, AEs leading to discontinuation, and serious AEs will be completed. For treatment-related AEs, these will also be presented by treatment/test site.

Detailed methodology for summary and statistical analyses of the data collected in this study will be documented in a Statistical Analysis Plan, which will be maintained and signed off prior to study unblinding.

| Document Name | G\$in:i2:071985t-prot@207 585 | | |
|----------------------|---|---------------------|----------------------|
| Туре | Version | Document Identifier | Effective Date |
| eldo climitralleatbo | 0.0; CURRENT; Most-Recent; Rfferietiwed | 090032d580e4@556 | 31-Jan-2017 14:20:06 |
| Reason For Issue | Auto Issue | | |

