3.4. Study Design and Application Amount Justification

Study Design:

This will be a single-center, randomised, assessor blind study in healthy subjects aged 18 to 65 years. Subjects will be exposed to repeated insult dermal semi-occlusive patch application of a cosmetic facial skin product and negative control (saline

| Document Name |   | | | |
|-----------------------|--|------------------|----------------------|--|
| Туре | Version Document Identifier Effective Date | | | |
| eldo climitarelleatoc | 0.0; CURRENT; Most-Recent; Revietived | 090032d580e42d66 | 31-Jan-2017 14:20:06 | |
| Reason For Issue | Auto Issue | | | |

solution).

Screening:

During screening subjects will sign an informed consent document and then a dermatological assessment will be conducted to ensure subjects have no dermatological conditions on their dorsum (backs) that might impact subject safety or study results and to ensure subjects have a Fitzpatrick Phototype I to IV.

Each subject's medical history and medication history will be reviewed, as well as inclusion/exclusion criteria. After which, site staff will review lifestyle guidelines and directions with eligible subjects.

Induction Phase:

Visit 2/Day 1 of the induction phase could be combined with Visit 1.

On Day 1 of the Induction Phase, eligible subjects will return to the study site and another dermatological assessment will be conducted to ensure subject continued eligibility (if Visits 1 and 2 are not combined), as well as a review of concomitant medications since screening. Test sites will be designated above the waist between the left scapula and waistline and away from the spinal mid-line. The site of application of the products will then be randomly assigned. Baseline grading/assessment of the test sites will then be performed.

There will be a total of 9 patch applications, over 3 consecutive weeks during the induction phase, with patches applied on alternate weekdays each week (Monday, Wednesday, and Friday). Each patch will contain the test product and saline solution. Each patch will remain in place for $48 (\pm 2)$ hours on weekdays and 72 hours on weekends. The patch will be removed and the area will be cleaned with saline solution. After 30 minutes (maximum of 1 hour) the site will be graded/evaluated as per the scale in Appendix 2. A new patch of both test product and saline solution will then be reapplied to the same site.

Rest Phase:

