9.3.3. Safety Analysis(es)

Adverse Events (AE) will be tabulated according to the current version of the MedDRA. Frequencies and percentages will be presented overall, for each system organ class, and for each preferred term. Summaries of treatment-emergent AEs, treatment-related AEs, AEs leading to discontinuation, and serious AEs will be completed. For treatment-related or treatment skin site related AEs, these will also be presented by product/test site.

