2.5.2 Safety

2.5.2.1 Adverse events and Serious Adverse Events

All adverse events (AEs) will be summarised by primary system organ class and preferred term.

Treatment emergent adverse events (TEAEs) will be summarized by the number and percentage of subjects having any adverse event, an adverse event in each System Organ Class, and each individual adverse event ([Table 14.3.1.1](#)). All TEAEs will also be tabulated by severity ([Table 14.3.1.2](#)). Treatment-emergent AEs suspected of a relationship to study medication and those causing study discontinuation will be presented in a similar manner ([Table 14.3.1.3](#)). For treatment-related AEs, these will also be presented by severity, if applicable ([Table 14.3.1.4](#)).

Additionally, all treatment-emergent adverse events will be listed.

Deaths occurring during treatment (if any) will be listed ([Listing 14.3.2.1](#)) by treatment, including the date and study day of death, and the principal cause of death. Non-fatal serious

Document Name	gsk-207585-reporting-and-analysis-plan		
Type	Version	Document Identifier	Effective Date
eldo_controlled	0.1; CURRENT; Most-Recent; Reviewed	090032d580e125d0	
Reason For Issue			

GSK Consumer Healthcare

Confidential

Page 12

Statistical Analysis Plan

207585

adverse events and adverse events causing study treatment discontinuation will be listed ([Listing 14.3.2.2](#)).

All AEs will be listed in the [Listing 16.2.7.1](#) and [Listing 16.2.7.2](#)

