Safety Population (N=xx)	System Organ Class Preferred Term	Facial micellar cleanser	Saline Solution	
		(N=XX)	(N=XX)	nAE
NUMBER OF SUBJECTS WITH AT LEAST ONE AE	xx (xx.x)	xx	xx (xx.x)	xx
NUMBER OF SUBJECTS WITH NO AE	xx (xx.x)	xx	xx (xx.x)	xx
SKIN RELATED AES	xx (xx.x)	xx	xx (xx.x)	xx
SKIN AND SUBCUTANEOUS TISSUE DISORDERS	xx (xx.x)	xx	xx (xx.x)	xx
ERYTHEMA	xx (xx.x)	xx	xx (xx.x)	xx
DERMATITIS	xx (xx.x)	xx	xx (xx.x)	xx
NON SKIN RELATED AES	xx (xx.x)	xx	xx (xx.x)	xx
GASTROINTESTINAL SYSTEM	xx (xx.x)	xx	xx (xx.x)	xx
ABDOMINAL PAIN	xx (xx.x)	xx	xx (xx.x)	xx
DRY MOUTH	xx (xx.x)	xx	xx (xx.x)	xx
VOMITTING	xx (xx.x)	xx	xx (xx.x)	xx

n (%) = Number (percent) of subjects nAE = Number of adverse events.

Page x of y

PPD

Document Name	gsk-207585-reporting-and-analysis-plan		
Type	Version	Document Identifier	Effective Date
elido_controlled	0.1; CURRENT; Most-Recent; Reviewed	090032d580e125d0	
Reason For Issue			

Protocol: 207585

Program Run Date:ddmonyyyy

 Table 14.3.1.2
 Summary of Treatment emergent Adverse Event by Severity
 Safety Population

Safety Population (N=xx)	System Organ Class Preferred Term	Facial micellar cleanser (N=xx)						Saline solution (N=xx)					
		Mild		Moderate		Severe		Mild		Moderate		Severe	
		n (%)	nAE	n (%)	nAE	n (%)	nAE	n (%)	nAE	n (%)	nAE	n (%)	nAE
NUMBER OF SUBJECTS WITH AT LEAST ONE AE		xx (xx.x)	xx	xx (xx.x)	xx	xx (xx.x)	xx	xx (xx.x)	xx	xx (xx.x)	xx	xx (xx.x)	xx
NUMBER OF SUBJECTS WITH NO AE		xx (xx.x)	xx	xx (xx.x)	xx	xx (xx.x)	xx	xx (xx.x)	xx	xx (xx.x)	xx	xx (xx.x)	xx
SKIN RELATED AES		xx (xx.x)	xx	xx (xx.x)	xx	xx (xx.x)	xx	xx (xx.x)	xx	xx (xx.x)	xx	xx (xx.x)	xx
SKIN AND SUBCUTANEOUS TISSUE DISORDERS		xx (xx.x)	xx	xx (xx.x)	xx	xx (xx.x)	xx	xx (xx.x)	xx	xx (xx.x)	xx	xx (xx.x)	xx
ERYTHEMA		xx (xx.x)	xx	xx (xx.x)	xx	xx (xx.x)	xx	xx (xx.x)	xx	xx (xx.x)	xx	xx (xx.x)	xx
DERMATITIS		xx (xx.x)	xx	xx (xx.x)	xx	xx (xx.x)	xx	xx (xx.x)	xx	xx (xx.x)	xx	xx (xx.x)	xx
NON SKIN RELATED AES		xx (xx.x)	xx	xx (xx.x)	xx	xx (xx.x)	xx	xx (xx.x)	xx	xx (xx.x)	xx	xx (xx.x)	xx
GASTROINTESTINAL SYSTEM		xx (xx.x)	xx	xx (xx.x)	xx	xx (xx.x)	xx	xx (xx.x)	xx	xx (xx.x)	xx	xx (xx.x)	xx
ABDOMINAL PAIN		xx (xx.x)	xx	xx (xx.x)	xx	xx (xx.x)	xx	xx (xx.x)	xx	xx (xx.x)	xx	xx (xx.x)	xx
DRY MOUTH		xx (xx.x)	xx	xx (xx.x)	xx	xx (xx.x)	xx	xx (xx.x)	xx	xx (xx.x)	xx	xx (xx.x)	xx
VOMITTING		xx (xx.x)	xx	xx (xx.x)	xx	xx (xx.x)	xx	xx (xx.x)	xx	xx (xx.x)	xx	xx (xx.x)	xx

n (%) = Number (percent) of subjects nAE = Number of adverse events.

Page x of y

PPD

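### The SAP's all-TEAE tables have only cleanser and saline columns although every subject wears both products, so overall AE incidence is not shown and non-site events have no assignment rule

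*SAP*

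**What the plan says.** **Design.** Protocol 3.4 and SAP 1.3 put both products in every patch: "Each patch will contain the test product and saline solution". Protocol 5.3 applies both to each subject's back, and only the location of each product is randomised (5.3.1).

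**Planned AE summary.** Protocol 9.3.3 says "Frequencies and percentages will be presented overall, for each system organ class, and for each preferred term", and then adds "For treatment-related or treatment skin site related AEs, these will also be presented by product/test site". The synopsis (Statistical Methods) is narrower: "For treatment-related AEs, these will also be presented by treatment/test site". SAP 2.5.2.1 describes the main table without any product split: "Treatment emergent adverse events (TEAEs) will be summarized by the number and percentage of subjects having any adverse event".

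**Shells.** SAP 5.1 gives two column labels, one per product. Tables 14.3.1.1 and 14.3.1.2 use only these, with the second subdividing each by severity. The rows include "NUMBER OF SUBJECTS WITH AT LEAST ONE AE", "NUMBER OF SUBJECTS WITH NO AE" and "NON SKIN RELATED AES", the last illustrated by abdominal pain, dry mouth and vomiting. Under SAP 4.2, Tables 14.3.1.3 and 14.3.1.4 reuse the same templates. Table 14.3.1.1 is a top-line output (SAP 4.4).

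**AE capture.** Protocol 7.4 uses a general question at each visit as one source of AEs. Protocol 6.2.2 and 7.1.1 have unusual reactions documented as AEs together with their effect on the test areas concerned. Appendix 2 captures a local patch response as an AE when it is more severe than expected. Causality is judged against the study product (7.3). Listing 16.2.7.1 is headed by treatment group.

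**The concern.** The layout is that of a parallel-group trial. Here the two columns hold the same people over the same exposure period, so neither the subject nor the timing of an event says which product it belongs to. A local reaction can be placed by its site; an episode of vomiting cannot. Without a rule, the person filling the shell has to invent one, and the choice decides what the any-AE and no-AE rows say.

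Two things are at stake. AE frequency and severity is the secondary endpoint, and the proportion of subjects with any AE is not presented as such in the table meant to report it. The side-by-side columns also invite a product comparison for events that have no product. Reactions that can be graded on Appendix 2 are generally kept out of the AE record, so non-site events may fill a good part of the table. Because unusual or unexpectedly severe local reactions are still recorded as AEs, the mix cannot be known in advance.

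**Working it through.** The plan states no figure on this point, so there is none to reproduce. The check has two parts.

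**1. Is the overall column really absent?** Each row of the Table 14.3.1.1 shell carries two pairs of entries (subjects with percentage, and number of AEs), one per product. Each row of Table 14.3.1.2 carries 2 × 3 pairs, two products by three severities. No entries are left for a third column, so this is not a fault of text extraction. Tables 14.1.1 and 14.1.2.1 in the same section do have an overall column.

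**2. How much can the assignment rule move the any-AE row?** The documents give no AE rates. Only N = 240 (the planned minimum randomised, taken here as the Safety population) comes from them; the rest is assumed:

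- S = 24 subjects with a non-site AE
- b = 6 with a cleanser-site AE
- c = 2 with a saline-site AE
- o = number of subjects with AEs at both sites; no site subject also has a non-site AE

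Overall incidence = (S + b + c − o)/N. With o = 0 this is 32/240 = 13.3%, leaving 240 − 32 = 208 subjects with no AE.

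| Rule for non-site events | Cleanser | Saline | No-AE row |
|---|---|---|---|
| Both columns: S+b, S+c | 30 (12.5%) | 26 (10.8%) | 210, 214 |
| Neither column: b, c | 6 (2.5%) | 2 (0.8%) | 234, 238 |
| All to cleanser: S+b, c | 30 (12.5%) | 2 (0.8%) | 210, 238 |
| All to saline: b, S+c | 6 (2.5%) | 26 (10.8%) | 234, 214 |

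The last two rows are bounds, not likely practice. Double entry is the likeliest rule. Under it the cleanser column is short by c − o subjects and the saline column by b − o:

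- o = 0: short by 2 (2/240 = 0.8 points) and 6 (6/240 = 2.5 points).
- o = 2: overall is 30/240 = 12.5%, equal to the cleanser column; saline is short by 4 (1.7 points).
- b = c = 0: both columns equal the overall rate, 24/240 = 10.0%. They are identical by construction and carry no information about the products.

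Varying S does not change the shortfall under double entry (o = 0):

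- S = 5: overall 13/240 = 5.4%; columns 11 (4.6%) and 7 (2.9%).
- S = 48: overall 56/240 = 23.3%; columns 54 (22.5%) and 50 (20.8%).

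**The case against.** **The consequence is small.** No formal inference is planned, and the irritation and sensitisation conclusions come from Tables 14.2.1.1 to 14.2.2.2. Listing 16.2.7.1 shows every AE by subject number and is itself a top-line output, so overall incidence can be rebuilt by counting unique subjects. All of this stands and limits the weight of the point. It does not justify a summary table that omits the quantity it exists to report.

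**The size rests on assumptions.** This also stands. The most striking contrasts, such as 12.5% against 0.8%, come from rules few would adopt. Under double entry the gaps are modest and vanish if there are no site AEs.

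**The no-AE row can be read per site.** Read that way, 234 and 238 under the neither rule are not false. But the shell labels the row as a count of subjects and has no footnote giving the per-site reading.

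**Attribution may be settled in the CRF.** The treatment-group heading of Listing 16.2.7.1 suggests that the AE record may carry a product field. A reader might infer that AEs are collected only at subject level and so can never be attributed. The documents do not support that: protocol 6.2.2, 7.1.1 and Appendix 2 link some AEs to test areas, and the CRF is not among the documents. What is established is that the protocol and SAP state no rule for events without a site.

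**There may be no conflict with the protocol.** A reader might infer that the SAP changed the planned analysis without declaring it, since SAP section 3 reports no changes. The text does not establish this. In protocol 9.3.3, presentation overall could mean the any-AE row, and requiring a product display for some AEs does not forbid it for others. The natural reading is still a pooled summary with an added split, and the text of SAP 2.5.2.1 fits that; only the shells depart from it.

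**Conclusion.** The point holds as a defect in the layout of the safety tables and should be corrected. With both products on every subject, two product columns alone do not show subject-level AE incidence, and events without a site have no stated place. That much follows from the documents and needs no assumed numbers.

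Its size depends on unknown AE counts. Under double entry each column misses the subjects whose only AE was at the other site: 0.8 and 2.5 points in the illustration, and nothing if there are no site AEs. Larger distortions need rules that are possible under the shells but unlikely. The damage is limited to descriptive tables; no test and no primary score table is affected.

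Separately, protocol 9.3.3 asks for the product/test-site display for related or skin-site AEs, while the synopsis mentions related AEs only. The two should be aligned.

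**What to change.** 1. Add an overall column, N = Safety population, to Tables 14.3.1.1 to 14.3.1.4, and report all TEAEs and the any-AE and no-AE rows there.
2. Keep product/test-site columns only for treatment-related AEs and test-site skin AEs.
3. State in SAP 2.5.2.1 that an event is assigned to a product only if it is localised to that product's test site or recorded as related to that product; otherwise it counts in the overall column only. Apply the same rule to Listing 16.2.7.1, so that every AE still appears there.
4. Align the protocol synopsis with section 9.3.3 on which AEs are shown by product/test site.
5. Check that the CRF captures product or test site for these AEs.

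The cost is shell edits and one sentence in the SAP, which is at version 0.1 and due to be finalised before database freeze and unblinding, plus the synopsis wording. No new data are needed if the CRF already records product or test site, which has to be confirmed.
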